8. STUDY POPULATION

8.1. Subject Disposition

Subject disposition information will be summarized and listed for all subjects. Summaries will include the following: the number of subjects randomized, the number of subjects in each analysis population, the number of subjects at each center, the number of subjects completing the DB phase (Week 24) and each scheduled visit (Week 2, 6, 12, 14, and 18), the primary reason for discontinuation from the DB phase, and the number of subjects enrolling in the LTSE. A subject will be considered as completing the DB phase (Week 24) and each scheduled visit (Weeks 2, 6, 12, 14, and 18) if the subject has a non-missing assessment of ALP at the corresponding visit. Percentages will be based on the ITT Population.

8.2. Protocol Deviations

Protocol deviations for missed visits, missed assessments, out of window visits or assessments, and violations of inclusion/exclusion criteria will be determined based on available data. All other protocol deviations will be collected by the clinical research associates. Major protocol deviations identified during the DB phase that could potentially affect the conclusions of the study or result in a subject's removal from an analysis population will be classified as such prior to database lock of the DB phase. Major protocol deviations will be summarized by deviation category and treatment group. All protocol deviations and their classifications will be presented in a listing. Subjects with protocol deviations that result in a subject's removal from the ITT, Safety, W12C, W24C, Per Protocol, or PK Populations will be flagged in a listing.

8.3. Demographic and Baseline Characteristics

Demographic variables will include the following:

- Age at informed consent
- Age at informed consent categorized as <65 years and ≥ 65 years
- Sex
- Race/Ethnicity

Other Baseline characteristics will include the following:

- Weight (kg)
- Height (cm)
- BMI (kg/m^2)
- BMI categorized as $<30 \text{ kg}/\text{m}^2$ and $\geq 30 \text{ kg}/\text{m}^2$
- Hepatic ultrasound to assess bile duct patency performed (Yes/No)
- Key liver function test results as a continuous variable and categorized as follows by the ULN and the LLN unless otherwise specified:
 - ALP: $\leq 3 \times \text{ULN}$, $>3 \times \text{ULN}$; and, $\leq \text{median baseline ALP}$, $> \text{median baseline ALP}$

- Total Bilirubin: \leq ULN, $>$ ULN, $>$ ULN - \leq 1.5xULN, $>$ 1.5xULN - \leq 2xULN, $>$ 2xULN - \leq 2.5xULN
- International normalized ratio (INR): \leq 1.3, $>$ 1.3 stratified by subjects on/not on anticoagulants at the time of randomization

Arithmetic summary statistics as described in [Section 6.2.1](#) will be presented for age, weight, height, BMI, and key liver function test results. Frequency counts and percentages will be presented for age groups, sex, race/ethnicity, BMI category, key liver function categories, and hepatic ultrasound.

Race and ethnicity will be summarized as follows:

- Race
 - American Indian or Alaska Native
 - Asian
 - Black or African American
 - Native Hawaiian or Other Pacific Islander
 - White
- Ethnicity
 - Hispanic or Latino
 - Not Hispanic or Latino
 - Not reported
 - Unknown

Demographic and Baseline characteristics will be summarized for the ITT, Safety, PK, W12C, and W24C populations. All demographic and Baseline characteristics will be presented in data listings. The subgroup tables will be generated for IBD, UC, and CD regardless of the total number of patients in each group. For the remaining subgroups, the tables will be generated as long as each subgroup contains at least 10% of the subjects in the overall population.

8.4. PSC Disease History

Baseline PSC disease characteristics will be summarized using data collected from the PSC Disease History eCRF. Assessments include the following:

- Age at first PSC diagnosis
- Age at first PSC diagnosis categorized as $<$ 40 years and \geq 40 years
- Symptomatic at diagnosis (Yes/No)
- Age at first occurrence of PSC symptoms
- Age at first occurrence of PSC symptoms categorized as $<$ 40 years and \geq 40 years
- Duration of PSC in years at time of informed consent

- Duration of PSC categorized as \leq median years and $>$ median years
- PSC diagnosis confirmed via cholangiography?
- Modality of PSC diagnosis (endoscopic retrograde cholangiopancreatography [ERCP], magnetic resonance cholangiopancreatography [MRCP], Other)
- Affected bile ducts (intra-hepatic, extra-hepatic, both, unknown)
- Symptoms of PSC (Never, Previous, Current)
 - Right upper quadrant abdominal pain
 - Fatigue
 - Weight loss
 - Jaundice
 - Pruritus
 - Other
- Severity of most recent pruritus event (Mild, Moderate, Severe)
- UDCA Use (Never/Previous/Current)
- Total daily dose of UDCA (mg/kg)
- Inflammatory Bowel Disease (IBD) (No IBD, Ulcerative Colitis, Crohn's Disease, Other)

Arithmetic summary statistics as described in [Section 6.2.1](#) will be presented for the age at first PSC diagnosis, age at first occurrence of PSC symptoms, duration of PSC, and total daily dose of UDCA (mg/kg). All other categorical PSC disease characteristics will be summarized using frequency counts and percentages. PSC disease history will be summarized for the ITT, W12C, and W24C Populations. The subgroup tables will be generated for IBD, UC, and CD regardless of the total number of patients in each group. For the remaining subgroups, the tables will be generated as long as each subgroup contains at least 10% of the subjects in the overall population. PSC disease history will be presented in a data listing.

8.5. General Medical History

Verbatim medical history terms on eCRFs will be mapped to preferred terms and system organ classes using the Medical Dictionary for Regulatory Activities (MedDRA) version 17.1. Frequency counts and percentages of the number of subjects reporting an abnormal Baseline medical history will be summarized by MedDRA system organ class and preferred term using the ITT Population.

Summaries that are displayed by system organ class and preferred term will be ordered by descending order of incidence of system organ class and preferred terms within each system organ class.

Medical history data will be presented in a data listing.

8.6. Prior and New Concomitant Medications

Verbatim terms on eCRFs will be mapped to ATC class and preferred term using the World Health Organization Drug Dictionary Enhanced (WHO-DDE June 2014).

Pretreatment medications are those medications with start and stop dates prior to the first dose of investigational product in the DB phase. Prior concomitant medications are those medications that started prior to, and continued after, the first dose of investigational product in the DB phase. New concomitant medications are those medications that were started after the first dose of investigational product in the DB phase. If it cannot be determined whether the medication was a new concomitant medication due to a partial start or stop date or if the medication is taken on the same date as the first OCA dose in the DB phase, then it will be counted as a new concomitant medication.

Pretreatment medications will be presented in listings only. Prior and new concomitant medications will be summarized by World Health Organization ATC class and preferred term using the ITT Population. New concomitant medications will be summarized separately. These summaries will present the number and percentage of subjects using each medication. Subjects may have more than one medication per ATC class and preferred name. A subject is counted once if one or more medication is reported at the ATC class or preferred term level. Each summary will be ordered by descending order of incidence, for all OCA treated patients, of ATC class and preferred term within each ATC class.

Prior and new concomitant medications will be presented a data listing.

9. EFFICACY ANALYSES

The primary and secondary efficacy analyses will be based on the ITT Population, W12C and W24C populations.

9.1. Primary Efficacy Analyses

The primary efficacy endpoint is the Week 24 change from Baseline in ALP. Using the ITT population, the primary efficacy analysis will compare the Week 24 change from Baseline in ALP between OCA 10 mg treatment group and placebo and OCA 3 mg treatment group and placebo using an ANCOVA model with treatment group, visit, and randomization strata as fixed effects, and Baseline ALP as a covariate.

In order, to provide estimates of the change from Baseline and corresponding 95% CI, the repeated measures ANCOVA methods described in [Section 6.2.3](#) will be applied. Model fit will be assessed in order to determine the validity of the estimates. The analysis will be repeated with percentage change from Baseline as the dependent variable. Estimates of least-square (LS) means, SEs, and 95% CIs will be presented by treatment group.

The values, change from Baseline, and percentage change from Baseline will be summarized using observed values by treatment group and visit using arithmetic summary statistics as described in [Section 6.2.1](#).

A hierarchical approach will be used for multiplicity adjustment across the primary efficacy endpoint for other visits and doses as described below. If the primary efficacy analysis is statistically significant ($p < 0.05$), the following order will be used in the testing procedure to compare the change from Baseline in ALP between OCA and placebo:

- Week 12: OCA 5 mg treatment group (randomized to 5 mg for the initial 12 weeks followed by 10 mg for the latter 12 weeks) vs. placebo
- Week 24: OCA 3 mg treatment group (randomized to 1.5 mg for the initial 12 weeks followed by 3 mg for the latter 12 weeks) vs. placebo
- Week 12: OCA 1.5 mg treatment group (randomized to 1.5 mg for the initial 12 weeks followed by 3 mg for the latter 12 weeks) vs. placebo

If at any step a comparison above is not statistically significant, then all subsequent comparisons will be exploratory rather than confirmatory.

Sensitivity analysis for the primary efficacy analysis will be performed using the W12C and W24C Populations. In addition, the arithmetic summary statistics will be presented by antibiotic use, IBD, UC, and CD subgroups as described in [Section 6.2.8](#).

An unblinded interim analysis of the primary endpoint will be conducted after approximately 50% of the subjects have completed the initial 12-weeks of blinded treatment. The interim analysis will use the same model described in [Section 6.2.3](#) on the change from Baseline ALP to Week 12 in addition to Week 24.

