#### 12.3.1. Primary Efficacy Analysis

The primary efficacy endpoint is the Week 24 change from Baseline in ALP. The primary efficacy analysis will compare the Week 24 change from Baseline in ALP between OCA 10 mg treatment group and placebo using an analysis of covariance (ANCOVA) model with fixed effects for treatment group and randomization strata, and Baseline as a covariate.

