6.2.3. Analysis of Covariance

Analysis of covariance (ANCOVA) will be performed to provide least square (LS) mean estimates and 95% two-sided confidence intervals (CIs) of the change and percentage change from Baseline at each DB post-Baseline visit. Model covariates include then randomization stratification values (ie, UDCA use [yes, no] and screening total bilirubin [$\leq 1.5 \times \text{ULN}$, $> 1.5 \times \text{ULN}$ – $< 2.5 \times \text{ULN}$]) and the Baseline of the parameter being estimated. The primary analysis will exclude the treatment by visit interaction term.

Normality/Equal Variance Testing

The assumption of a random error component being normally distributed will be tested by examining skewness and kurtosis following D'Agostino et al. (1990) with the residuals pooled over treatments. Additionally, homogeneity of variances across treatment groups will be examined using Levene's Test (Glaser 1982) with significance level of 0.05, based on absolute values of the residuals from the residual medians for each treatment. The data will be determined non-normal if the p-value for either the D'Agostino Skewness Test or D'Agostino Kurtosis Test is less than 0.05. If the data do not meet the normality or homogeneity assumptions of the parametric analyses, then a RT-2 rank transformation will be applied to the data (CFB endpoint and baseline value). To minimize the effect of differing study site sizes, the ranks will be standardized to lie between 0 and 1 using the NPLUS1 option of SAS® PROC RANK. Tied values will receive the mean value (midranks) of the corresponding ranks.

Example SAS® code for the primary analysis is as follows:

```
ODS graphics on;  
proc mixed data=ADLB noclprint plots=residualpanel;  
  class ucdafl tbilfl trt;  
  model change=Baseline ucdafl tbilfl trt / ddfm=kr;  
  lsmeans trt / cl diff alpha=0.05;  
  title1 "Linear Mixed Effects Model Based Estimates of XXXX Means";  
  title2 " Fixed Effects for Visit, Randomization Strata, and Treatment and Baseline as  
  Covariates";  
run;  
ODS graphics off;  
quit;
```

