6.2.7. Multiple Comparisons/Multiplicity

A hierarchical approach will be used for multiplicity adjustments. If the primary efficacy analysis is statistically significant ($p < 0.05$), the following order will be used in the testing procedure to compare the change from Baseline in ALP between OCA and placebo:

- Week 12: OCA 5 mg treatment group (randomized to 5 mg for the initial 12 weeks followed by 10 mg for the latter 12 weeks) vs. placebo
- Week 24: OCA 3 mg treatment group (randomized to 1.5 mg for the initial 12 weeks followed by 3 mg for the latter 12 weeks) vs. placebo
- Week 12: OCA 1.5 mg treatment group (randomized to 1.5 mg for the initial 12 weeks followed by 3 mg for the latter 12 weeks) vs. placebo

If at any step the comparison is not statistically significant, then all subsequent comparisons will be exploratory rather than confirmatory.

Multiplicity adjustments will not be applied for any other statistical testing.

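### SAP 9.1 puts 3 mg versus placebo at Week 24 both inside the primary comparison and behind it in the hierarchy, does not say which contrast opens the hierarchy, and misdescribes the model

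*SAP*

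**What the plan says.** Protocol 12.3.1 sets a single primary contrast: "The primary efficacy analysis will compare the Week 24 change from Baseline in ALP between OCA 10 mg treatment group and placebo". The model has treatment group, randomization strata and Baseline. Protocol 12.3.2 then lists three ordered follow-on tests: 5 mg at Week 12, 3 mg at Week 24, and 1.5 mg at Week 12, each against placebo.

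SAP 5.1.1 keeps the same endpoint. In SAP 9.1, however, the stated purpose of the primary analysis is to "compare the Week 24 change from Baseline in ALP between OCA 10 mg treatment group and placebo and OCA 3 mg treatment group and placebo". These comparisons are to be made "using an ANCOVA model with treatment group, visit, and randomization strata as fixed effects, and Baseline ALP as a covariate". Its next paragraph refers the reader to 6.2.3 for "the repeated measures ANCOVA methods described in" that section.

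SAP 9.1 introduces the hierarchy with the sentence "A hierarchical approach will be used for multiplicity adjustment across the primary efficacy endpoint for other visits and doses as described below". In both 9.1 and 6.2.7 the condition for starting it is "If the primary efficacy analysis is statistically significant", and the second step is "Week 24: OCA 3 mg treatment group (randomized to 1.5 mg for the initial 12 weeks".

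The example code in SAP 6.2.3 reads "model change=Baseline ucdafl tbilfl trt / ddfm=kr". It has no visit term and no REPEATED statement, although its title line mentions visit. Repeated measures are described in 6.2.4. SAP 11, the list of changes from the protocol, mentions only microbiome and genetic samples.

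**The concern.** The sentence in SAP 9.1 defines the test that opens the confirmatory hierarchy, and it has three faults.

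1. **Contrast.** 3 mg versus placebo at Week 24 is named in the primary analysis and is also a step that may be taken only after that analysis succeeds. It cannot be both. Because the opening condition names no contrast, the text does not exclude opening the hierarchy on either dose, or only on both.
2. **Visit term.** Neither the protocol model nor the 6.2.3 MODEL line contains visit. For a Week 24 response the term is constant and does nothing. If several visits were fitted without an interaction, the model would estimate one treatment effect averaged over visits, although the dose rises at Week 12. That is not the protocol's endpoint.
3. **Pointer.** The repeated-measures methods are in 6.2.4, not 6.2.3.

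The rules left open differ in type I error and power from the protocol's rule. SAP 9.2, 9.2.2, 9.2.3 and 9.3.1 reuse the primary model or 6.2.3, so the model ambiguity carries over to them.

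**Working it through.** **Inputs.** SAP 4 gives mean changes of -20 and -5 (difference 15), SD 16, two-sided alpha 0.05, 25 per arm and 20% dropout, so 25 × 0.8 = 20 evaluable. The 3 mg effect is not given. It is assumed here to be one-third, half, two-thirds or all of the 10 mg effect.

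**Reproducing the plan's power.** Two-group t-test, noncentrality = 15 / (16 × √(2/n)).

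- n = 25: 15 / 4.525 = 3.31 on 48 df, power 90.1%. The stated 90% reproduces.
- n = 20: 15 / 5.060 = 2.96 on 38 df, power 82.4%.

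**Possible opening rules.** The two dose contrasts share the placebo arm. Each has variance 2σ²/n and their covariance is σ²/n, so their correlation is 0.5. Three arms were simulated with pooled variance, each contrast tested at two-sided 0.05. Entries are percentages for 25 / 20 evaluable per arm.

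| Opening rule | False opening, neither dose works | Power, 3 mg effect one-third | half | two-thirds | equal |
|---|---|---|---|---|---|
| 10 mg only | 5.0 / 5.0 | 90.5 / 82.9 | 90.5 / 82.9 | 90.5 / 82.9 | 90.5 / 82.9 |
| Either dose | 9.1 / 9.0 | not run | 91.2 / 84.3† | not run | 96.9† / 92.9† |
| Both doses | 1.0† / 1.0† | 19.1 / 15.7 | 36.5 / 29.5 | 56.7 / 46.1 | 84.0 / 73.0 |

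Unmarked cells use 1,000,000 draws and 3n - 6 df. Cells marked † come from a second run of 400,000 draws with 3n - 3 df. Where the two runs overlap they agree within 0.2 point.

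Checks on the 9%:

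- A bivariate normal with correlation 0.5 gives 9.07%.
- Independent tests would give 1 - 0.95² = 9.75%.
- Fitted ANCOVAs with two strata and Baseline (20,000 trials) give 9.0% (n = 25) and 9.3% (n = 20).

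**Visit term.**

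- On Week 24 rows only, ANCOVA with and without a constant visit column gives the same estimate, the same standard error (4.653 in the test data) and the same 69 residual df.
- If instead all six post-Baseline visits were fitted without a REPEATED statement, the true level of a nominal 5% test would be about 2[1 - Φ(1.96 / √(1 + 5ρ))]. That is 29% for an assumed within-subject correlation ρ of 0.5 and 40% for 0.9. SAP 6.2.3 does not clearly ask for such a fit. The figure only shows why the wording should not allow it.

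**The case against.** The strongest reply is that the intended rule can be recovered. The ordered list omits exactly one dose-by-visit contrast, 10 mg at Week 24, and SAP 9.1 says the hierarchy covers other visits and doses. If both doses were required, the later 3 mg step could never fail; if either sufficed, the same contrast would be tested twice. Only 10 mg as sole opening test makes the list coherent, and the protocol says exactly that. Protocol Appendix G shows that the Week 24 primary comparison was deliberately narrowed from both doses to 10 mg, so the 3 mg clause may be leftover wording. A three-arm model reports both contrasts anyway. The trial is a Phase 2 proof of concept, and no section states an either-dose or both-doses rule.

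All of this stands as evidence of intent, and it supports the proposed correction. It also means that no inflation of type I error has been shown under the likely reading. It does not make the text correct: reaching that reading requires setting aside the SAP's own definition of its primary analysis.

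On the visit term, the reply cuts the other way. SAP 6.2.3 says the primary analysis omits the treatment-by-visit interaction, a remark that makes sense only for multi-visit data. Calling the term harmless therefore depends on fitting Week 24 records alone. The wrong pointer and the code title are editorial.

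**Conclusion.** The point holds: SAP 9.1 is wrong as written and should be corrected. It departs from protocol 12.3.1 without declaring a change, and it contradicts its own hierarchy.

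Under the likely intent (a Week 24 ANCOVA, 10 mg versus placebo as sole opening test) the numerical effect is nil. Under the readings the text leaves open, false opening rises from 5% to about 9% (either dose). If both doses are required, opening power with 25 evaluable per arm falls from about 90% to between 19% and 84%. The error figures assume that neither dose works. The power figures rest on the SAP's 15 and 16 and on an assumed 3 mg effect. They illustrate what an unnamed opening test allows and do not forecast the trial's error rate.

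**What to change.** In SAP 9.1, define the primary test as Week 24 change from Baseline in ALP, 5-to-10 mg group versus placebo, by ANCOVA with treatment, UDCA stratum, bilirubin stratum and Baseline ALP. Delete the 3 mg clause, the visit effect and the repeated-measures reference from the primary text.

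State in 9.1 and 6.2.7 that only this test opens the hierarchy, and keep 3 mg at Week 24 at its listed step. In 6.2.3, remove visit from the code title, say that the primary fit uses Week 24 records only, and drop or reword the remark about the interaction. Keep the 6.2.4 mixed model as supportive; Appendix A already gives it its own ALP table (14.2.2.1).

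If the sponsor does want 3 mg as a co-primary contrast, the SAP must state the rule, control alpha for it, and list it in section 11.

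The cost is SAP wording only, to be settled before the double-blind database lock. The 6.2.3 MODEL line, run on Week 24 records, already gives the protocol's test; data collection, sample size and conduct do not change.

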6.2.4. Analysis of Covariance (Repeated Measures)

Analyses of the clinical laboratory values will also be carried out using a restricted maximum likelihood (REML) based repeated measures linear mixed model (MMRM) to evaluate the effect over time by providing LS mean estimates, 95% CIs of change and percentage change from Baseline at each DB post-Baseline visit. Model covariates include then randomization stratification values (ie, UDCA use [yes, no] and pre-randomization total bilirubin [$\leq 1.5 \times \text{ULN}$, $> 1.5 \times \text{ULN} - < 2.5 \times \text{ULN}$]), Baseline of the parameter being estimated, and a treatment by visit interaction term. An unstructured (5×5) covariance model will be used. If the computational algorithm fails to converge, the following structures will be executed: heterogeneous Toeplitz, Toeplitz, heterogeneous First-Order Autoregressive [AR (1)], heterogeneous compound symmetry (HCS), and compound symmetry (CS). The covariance structure converging to the best fit, as determined by Akaike's information criterion (AIC), will be used. The Kenward and Roger method will be used to calculate the denominator degrees of freedom for the test of fixed effects.

Example SAS® code for the ANCOVA with repeated measures is as follows:

```
ODS graphics on;  
proc mixed data=ADLB noclprint plots=residualpanel;  
  class subjid week ucdafl tbilfl trt;  
  model change=week Baseline ucdafl tbilfl trt trt*week/ ddfm=kr;  
  repeated week / subject=subjid type=uns;  
  lsmeans trt trt*week / cl diff alpha=0.05;  
  title1 "Linear Mixed Effects Model Based Estimates of XXXX Means by Visit";  
  title2 " Fixed Effects for Visit, Randomization Strata and Baseline as Covariates, and  
  Treatment by Visit Interaction";  
run;  
ODS graphics off;  
quit;
```

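### SAP 9.1 and 6.2.3 do not state one coherent primary model for the Week 24 ALP test; one of three possible readings pools the effect over visits

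*SAP*

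**What the plan says.** - **SAP 9.1.** "the primary efficacy analysis will compare the Week 24 change from Baseline in ALP", for OCA 10 mg and also OCA 3 mg against placebo, using an "ANCOVA model with treatment group, visit, and randomization strata as fixed effects, and Baseline ALP as a covariate". For the estimates and confidence intervals it then invokes "the repeated measures ANCOVA methods described in" Section 6.2.3.
- **SAP 6.2.3.** This is the plain ANCOVA section. It promises LS means "of the change and percentage change from Baseline at each DB post-Baseline visit", and adds: "The primary analysis will exclude the treatment by visit interaction term". The example code for the primary analysis has the line "model change=Baseline ucdafl tbilfl trt / ddfm=kr", while its output title reads "Fixed Effects for Visit, Randomization Strata, and Treatment and Baseline as" covariates. The code has no `REPEATED` statement and no `WHERE` or `BY` restriction to a visit.
- **SAP 6.2.4.** The repeated-measures model is here: "model change=week Baseline ucdafl tbilfl trt trt*week/ ddfm=kr", with a `REPEATED` statement. It is introduced as a further analysis and has its own ALP table (14.2.2.1, labelled MMRM).
- **Protocol 12.3.1.** The Week 24 ANCOVA has treatment and randomization strata as fixed effects and Baseline as covariate. It has no visit term and compares only OCA 10 mg with placebo.
- **SAP 11.** The only change listed concerns microbiome and genetic samples.

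**The concern.** The primary test decides whether the rest of the hierarchy is confirmatory, so its model should follow from the SAP without interpretation. Here it does not. A model fitted to Week 24 records alone cannot estimate a visit effect, and a sentence excluding treatment by visit has a function only if several visits are modelled together. Yet the endpoint is a single-visit one, and the MODEL line has no visit term.

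The dose doubles after Week 12, so a treatment effect averaged over visits is in general not the Week 24 effect. The hierarchy also tests each OCA arm at both Week 12 and Week 24, which requires a separate estimate at each visit. The programmer must decide which passage governs, and the SAP leaves that decision open.

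**Working it through.** **Step 1: the three readings.**

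| Reading | Text for it | Text against it | What it estimates |
|---|---|---|---|
| (a) ANCOVA fitted by visit | Week 24 endpoint (5.1.1, 9.1); Week 12 and Week 24 hierarchy (6.2.7, 9.1); interim text in 9.1 applying the 6.2.3 model to Week 12 and Week 24; per-visit estimates in 6.2.3; MODEL line; 9.2 reuses the primary ANCOVA, and Table 14.2.4.1 reports it by visit, apart from the MMRM | visit term and repeated-measures label in 9.1; exclusion sentence and code title in 6.2.3 | Week 24 difference |
| (b) 9.1 meant to cite 6.2.4 | visit term and repeated-measures label in 9.1; heading and model of 6.2.4 | exclusion sentence in 6.2.3; MMRM presented as additional; no change declared in Section 11 | Week 24 difference, through `trt*week` |
| (c) visit main effect, no interaction | visit term in 9.1 plus exclusion sentence in 6.2.3 | everything listed for (a) | one effect common to all visits |

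**Step 2: what (c) returns.** With a visit main effect and no interaction there is one treatment coefficient per OCA arm. It is a weighted mean of the visit-specific differences, Σ w_j δ_j with Σ w_j = 1. SAP Section 3 gives six visits: Weeks 2, 6, 12, 14, 18 and 24. The first three fall on the starting dose. The four ordered tests involve two arms (5/10 mg and 1.5/3 mg), so (c) supplies two distinct coefficients for four tests.

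**Step 3: the input difference.** The plan states no figure for this issue, so I take the difference from its sample-size section: −20 against −5, hence 15, with SD 16. With 25 per group, 15 / (16 × √(2/25)) = 3.31. That gives two-sided power of 0.912 by the normal approximation and 0.901 by the exact t, which reproduces the stated 90% without dropout. At 20 evaluable per group the figures are 0.842 and 0.824, a separate matter.

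**Step 4: illustration of (c) only.** Assume that the effect at Weeks 2, 6 and 12 is a fraction f of the Week 24 effect, and that the full effect is present at Weeks 14, 18 and 24. With complete data and equal weights (1/6 each), the starting-dose visits carry 3/6 = 0.5, so the estimate is 15 × [1 − 0.5 × (1 − f)].

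- f = 0.5: 15 × 0.75 = 11.25
- f = 0.75: 15 × 0.875 = 13.1
- f = 1: 15

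**Step 5: sensitivity.** All of these are assumptions.

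- 20% dropout, taken as linear, under independent, compound-symmetric or AR(1) errors: 10.8–11.0 at f = 0.5 and 12.9–13.0 at f = 0.75.
- SD rising from 13 to 16 over the visits with correlation 0.5: 9.4 at f = 0.5.
- Effect building up over 8 weeks at each dose level instead of stepping: 8.8 and 10.6 at f = 0.5 and 0.75.

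Reading (a) targets 15 in every case.

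**The case against.** The strongest reply is that 9.1 already fixes the response as the Week 24 change. With one visit in the data, the visit factor has a single level and drops out, leaving the protocol's ANCOVA. No example code in the SAP fits a visit main effect without the interaction. Reading (c) has to be assembled from one word in 9.1 and one sentence in 6.2.3, and it would make the hierarchy unworkable, which suggests that nobody meant it. That stands as evidence of intent, and it is why (a) is the best-supported reading. It does not make the text coherent: the visit term, the repeated-measures label and the exclusion sentence then have no function.

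A second reply is that the cross-reference is simply wrong and 6.2.4 was meant. That is possible, and it would still give a valid Week 24 contrast. It would also replace the protocol's primary analysis without being declared in Section 11.

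A third reply is that f is not anchored in PSC data. That is correct. The nearest figures in the documents are the Phase 3 PBC mean reductions in Protocol 4.4: 39% (10 mg), 33% (5-to-10 mg titration) and 5% (placebo). They give (33 − 5)/(39 − 5) = 0.82, hence 15 × [1 − 0.5 × 0.18] ≈ 13.7. The titration arm mixes doses, so this is only a rough guide.

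A reader might infer that the SAP has replaced the Week 24 endpoint with a pooled effect, or that the example code is to be run on all visit records as if they were independent. The documents support neither. The endpoint is stated as Week 24, and 6.2.3 promises estimates visit by visit.

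**Conclusion.** The point holds as a specification fault in the confirmatory test: SAP 9.1 and 6.2.3, taken together, do not define one primary model, and no departure from Protocol 12.3.1 is declared. Readings (a) and (b) both target the Week 24 difference. Only (c) does not; it equals that difference only if the effect is constant over time, and it cannot separate the Week 12 and Week 24 tests.

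The loss from 15 to about 11–13 applies to (c) alone. It rests on complete data, equal visit weights and an assumed starting-dose effect of 50–75% of the Week 24 effect. It does not estimate an error in the analysis that was probably intended. The text should be corrected before the double-blind database is locked.

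**What to change.** In SAP 9.1:

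- Delete the visit term and the repeated-measures label.
- Limit the primary comparison to OCA 10 mg against placebo, and leave OCA 3 mg at its place in the hierarchy (third of the four ordered tests).
- State that the ANCOVA, with treatment group and randomization strata as fixed effects and Baseline ALP as covariate, is fitted to Week 24 records for the Week 24 tests and separately to Week 12 records for the Week 12 tests.

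In SAP 6.2.3:

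- Delete the sentence on the treatment-by-visit term.
- Remove Visit from the code title.
- Add the visit restriction to the example code.

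Keep the 6.2.4 MMRM as supportive. If the sponsor did intend it as primary, Section 11 must declare that change.

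The cost is a few sentences and one line of code, with no new data. These edits align the primary model terms and comparison with Protocol 12.3.1. They do not deal with other features of 6.2.3, such as the switch to a rank transformation, which is a separate matter.
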